### 9.7.3 Comparative analyses

*The following relates to primary and secondary objectives.* These analyses will be conducted on the cohort to evaluate the effect of valproate on NDD, including ASD (see cohort definition in section 9.2.2 and 9.2.2.1) and on the cohort to evaluate the effect on CM (see cohort definition in section 9.2.2 and 9.2.2.2). Fathers who switch to or switch from an AED other than valproate, lamotrigine or levetiracetam, even if on monotherapy, will be excluded from the comparative analyses (as reported in section 9.3.1) (further details are provided in the multivariate analysis section 9.7.3.2).

For the *comparative analyses*, offspring maternally exposed to AEDs (including valproate, lamotrigine and levetiracetam) *in utero*, or during 3 months prior conception, as well as offspring from a mother with a history of epilepsy, will be excluded. For the *comparative analyses related to the primary outcome*, offspring exposed to AEDs and/ or diagnosed with epilepsy after birth will be excluded.

#### 9.7.3.1 Univariate analyses

Univariate analysis for each cohort will be performed to characterise exposure groups (valproate and lamotrigine/levetiracetam (composite and separately) in monotherapy) with respect to potential covariates. Additionally, univariate analysis will be used to assess the strength of the relationship of any potential confounders to the primary (NDD including ASD) and secondary (CM) outcomes. Differences between categorical variables will be tested using Fischer's Exact test OR Chi-squared test (depending on event counts), and differences between continuous variables will be tested by using parametric two sample t-tests, where appropriate. All risk and incidence estimates will be reported with a 95% CI. Significance level will be set to  $p < 0.05$  using 2-sided testing.

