The populations at study will include each individual offspring (or non-live birth) as the unit for analysis, therefore if the mother and father have more than one offspring they can be included more than once in the study; each offspring/non-live birth will coincide with the linked triple offspring/non-live birth, mother and father. Furthermore all variables collected for fathers and mothers will be re-calculated for each pregnancy.

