### **9.7.3.2.1 Effect estimation - Neurodevelopmental disorders, including autism**

A crude and a propensity-score (PS) weighted (section 9.7.3.2.3) Cox PH regression model will be used to estimate the HR of NDD, including ASD, with 95% CI (using offspring's calendar age in years as the underlying timescale) in offspring paternally exposed to valproate monotherapy within 3 months prior to LMP2 date compared to the reference group comprised of offspring paternally exposed to lamotrigine or levetiracetam (composite monotherapy) in the same time period. Inclusion of covariates not retained in the PS (section 9.7.3.2.2), in the Cox PH model will be considered in the event of imbalance in prognostically important variables. Covariates measured after index date will be included as time dependent in the Cox PH model, as appropriate. Post-estimation model diagnostics will be undertaken for each final parsimonious model, including log-log plots and Schoenfeld residuals, to assess the proportionality assumption.

Multiple offspring per father is possible and will introduce within-family dependencies into the data. Therefore in the analyses, paternal clustering will be taken into account by correcting standard errors with sandwich estimators (38). For purposes of the primary objective analysis for which the study is powered, a first Cox PH model will be estimated irrespective of clusters classification (section 9.3.1.3). This approach has the limitation to ignore intensity of exposure in the two exposure groups. To overcome this limitation, the first model will be repeated including the exposure intensity variable (estimated based on clusters as by application of k-means methodology (section 9.3.1.3)) as an effect modifier, i.e. the interaction exposure\*k-means will be included in the model. This second approach has the advantage of providing an estimate of the effect of paternal exposure to valproate vs the comparator group stratified by exposure intensity as measured by the k-means clusters.

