#### **9.7.4 Exploratory objective analyses**

For the *exploratory analyses*, offspring maternally exposed to AEDs (including valproate, lamotrigine and levetiracetam) *in utero*, or during 3 months prior conception, as well as offspring from a mother with a history of epilepsy, will be excluded. For the *exploratory analyses related to the primary outcome*, offspring exposed to AEDs and/or diagnosed with epilepsy after birth will be excluded.

For exploratory objective 5, for offspring paternally exposed to AED polytherapy, summary cohort characteristics and univariate analysis (section 9.7.3.1) will be performed to describe the putative risk factors and frequency of the primary composite outcome (NDD, including ASD) and for the secondary composite outcome (CM) for offspring paternally exposed to valproate (in combination with other AEDs excluding lamotrigine and levetiracetam) and offspring paternally exposed to levetiracetam/lamotrigine in polytherapy (i.e. polytherapy including at least one of them, and excluding valproate) at the time of conception.

For exploratory objective 6, to explore potential for unmeasured family-related confounding factors (such as genetic liability for neuropsychiatric conditions or congenital malformations and early postnatal environmental influences), an exploratory sibling-matched descriptive analyses will be conducted, separately, on the primary composite outcome (NDD, including ASD) and the secondary composite outcome (CM) whereby only families with paternal valproate exposure-discordant siblings will be included (at least one offspring with paternal valproate exposure and one offspring without exposure). For this analysis, summary cohort characteristics and univariate analysis (section 9.7.3.1) will be performed to describe the subgroups and identify potential risk factors for the composite primary and secondary outcomes of interest, respectively.

For exploratory objective 7, which is to investigate the risk of CM in live offspring paternally exposed to valproate (monotherapy), compared to lamotrigine or levetiracetam (composite monotherapy) treatment at the time of conception in Sweden, the descriptive (section 9.7.2), and comparative (section 9.7.3.2) analyses will be presented separately. This is because the population for analysis is comprised of live births only and therefore is systematically different to the cohorts for CM analysis in Norway and Denmark

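### The univariate tests in section 9.7.3.1 treat siblings as independent, so stable parental characteristics are compared between exposure groups at a true level above 5%

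*Protocol*

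**What the plan says.** - Section 9.7.3.1 sets the purpose: "Univariate analysis for each cohort will be performed to characterise exposure groups". It also asks how strongly potential confounders relate to NDD and CM.
- The tests are named: "Differences between categorical variables will be tested using Fischer's Exact test OR Chi-squared test (depending on event counts"), and for continuous variables "differences between continuous variables will be tested by using parametric two sample t-tests, where appropriate". The level is 0.05, "using 2-sided testing". Risks and incidences get 95% confidence intervals. The section makes no allowance for siblings.
- Section 9.7.1 makes the offspring the unit of analysis, so "if the mother and father have more than one offspring they can be included more than once in the study". It adds that "all variables collected for fathers and mothers will be re-calculated for each pregnancy".
- Section 9.7.3.2.1 (Cox model) states: "Multiple offspring per father is possible and will introduce within-family dependencies into the data", and prescribes sandwich standard errors. The same provision appears for the logistic model (9.7.3.2.2) and in sensitivity analysis 6 (9.7.5), and nowhere else.
- Section 9.7.4 reuses the univariate tests for exploratory objectives 5 and 6. For the exposure-discordant siblings of objective 6, "summary cohort characteristics and univariate analysis (section 9.7.3.1) will be performed to describe the subgroups and identify potential risk factors".

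**The concern.** A chi-squared or two-sample t-test takes its null distribution from independent observations. If a father keeps the same drug and the same lifetime diagnosis across his children, each further child repeats both variables and adds no new information, but the test counts it as if it did.

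The p-values from section 9.7.3.1 describe how the exposure groups differ and support the search for risk factors (secondary objectives 3 and 4). Some declared differences would then be the same fathers counted again. In objective 6, the reason for the analysis is to address unmeasured family factors, yet the named tests ignore which children belong to the same family.

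**Working it through.** **Inputs.** From the protocol: the tests and two-sided 0.05 (9.7.3.1), the offspring as unit (9.7.1), and lifetime paternal and maternal diagnoses among the factors (Tables 2 and 4). Not in the protocol: children per father and the within-father correlation (ICC). Both are assumed below and varied.

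**Nominal level reproduced.** With one child per father the formula gives 0.0500. Simulation (4,000 runs, 740 fathers) gave 0.047 for the t-test and 0.050 for chi-squared.

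**Formula.** With exposure constant within father, the design effect is D = 1 + (m′ − 1) × ICC, where m′ = E[m²]/E[m] and m is the number of children per father. The true level is 2(1 − Φ(1.96/√D)).

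**Worked case.** Suppose 70%, 25% and 5% of fathers have 1, 2 and 3 children:

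- E[m] = 0.70 + 0.50 + 0.15 = 1.35
- E[m²] = 0.70 + 1.00 + 0.45 = 2.15
- m′ = 2.15/1.35 = 1.593
- at ICC 1, the level is 2(1 − Φ(1.96/√1.593)) = 0.120, or 2.4 times nominal

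| Assumed shares with 1/2/3(/4) children | Mean | m′ | ICC 1 | ICC 0.5 | ICC 0.2 |
|---|---|---|---|---|---|
| 90/9/1 | 1.11 | 1.216 | 7.6% (1.5×) | 6.3% | 5.5% |
| 80/18/2 | 1.22 | 1.393 | 9.7% (1.9×) | 7.3% | 5.9% |
| 70/25/5 | 1.35 | 1.593 | 12.0% (2.4×) | 8.5% | 6.4% |
| 60/32/8 | 1.48 | 1.757 | 13.9% (2.8×) | 9.5% | 6.8% |
| 50/40/10 | 1.60 | 1.875 | 15.2% (3.0×) | 10.2% | 7.1% |
| 30/45/20/5 | 2.00 | 2.350 | 20.1% (4.0×) | 13.0% | 8.2% |

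A level of 10% to 15% (2 to 3 times nominal) needs D between 1.42 and 1.85.

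**Simulation.** At ICC 1 the t-test and chi-squared rates were:

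- 80/18/2: 9.5% and 9.0%
- 70/25/5: 11.6% and 12.5%
- 50/40/10: 15.3% and 16.6%

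With 50/40/10 and 20% of children given a redrawn exposure, the rates fell to 11.8% and 10.6%. With 50/40/10 and ICC 0.2 on the underlying continuous scale they were 6.1% and 5.2%, against 7.1% from the formula, so the low-correlation column is approximate. In a separate simulation of about 1,178 offspring, a father-clustered score test held 4.6% to 5.7% throughout.

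**Tests against NDD or CM.** The outcome's sibling correlation then takes the place of the exposure's. It is lower than for a drug that stays constant, so D lies closer to 1. The documents give no value for it.

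**Objective 6.** Take one exposed and one unexposed sibling in each of n families. The true variance of the mean difference is 2σ²(1 − ICC)/n, but the two-sample test uses 2σ²/n. The ratio is 1 − ICC, which is below 1. At ICC 0.2 it is 0.8, and the level is 2(1 − Φ(1.96/√0.8)) = 2(1 − Φ(2.191)), about 2.8%. The unpaired test is conservative here.

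**The case against.** **The size is not in the documents.** Eligibility limits repeat siblings. Each pregnancy must qualify separately: singleton, non-IVF and linked (9.2.2), with the father on one AED in that pregnancy's own window (9.3.1) and the mother free of AEDs and epilepsy (9.7.3). Study periods are also bounded (9.2.1). This stands: any multiplier is an assumption and must carry its range.

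**Parental variables are re-calculated for each pregnancy.** Age, recent medication and pregnancy-specific conditions can differ between siblings. This stands for those variables and lowers their inflation. It does not help lifetime diagnoses, which remain positive for later children once recorded.

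**Little depends on these p-values.** Propensity-score candidates enter by the size of the odds ratio or relative risk (above 1.1 or below 0.9), the score model is chosen on weighted balance (9.7.3.2.3), and the Cox and logistic estimates are already clustered. Objective 3 is descriptive. This stands and limits the consequence.

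**The sandwich provision may be meant for every analysis, or be left to the SAP.** This is weaker. The provision sits in the Cox section, is written out again for the logistic model, and corrects standard errors; Fisher's exact test has none to correct. The protocol also does more than defer: it names the unclustered tests and their level.

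**What a reader might wrongly infer.** One might conclude that all the univariate tests reject two to three times too often, that the primary result is compromised, or that objective 6 over-rejects as well. The documents support none of these. The multiplier needs family sizes and correlations they do not give, the primary model is corrected, and the direction in objective 6 is the reverse for exposure comparisons.

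**Conclusion.** The point holds in a limited form. The tests in section 9.7.3.1 are inconsistent with the protocol's own statement that offspring of one father are dependent. For parental characteristics stable across siblings, compared between exposure groups, the true level exceeds 5%. It is about 2 to 3 times nominal if drug and characteristic are constant and fathers contribute roughly 1.25 to 1.6 children on average, and about 1.1 to 4 times over means of 1.1 to 2.0 and ICC of 0.2 to 1. All of these inputs are assumptions.

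What is affected is the descriptive p-values, the confidence intervals that have no stated clustering, and, to a smaller degree, the risk-factor tests against the outcomes. In objective 6 the fault is the discarded matching. The change is worth making because it is cheap and the protocol already accepts the principle.

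**What to change.** In section 9.7.3.1, replace the named tests by father-clustered ones: regression or GEE with sandwich errors clustered on father, or a Rao-Scott chi-squared test. Apply the same clustering to the 95% confidence intervals for risks and incidences. Objective 5 and sensitivity analysis 11b refer to this section and would follow.

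For objective 6, and its replication in sensitivity analysis 11c, specify within-family methods such as conditional or family-stratified models. These also handle families with more than two siblings, which a simple McNemar test does not do directly.

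Reporting standardised differences for group characteristics in place of p-values is an option, not a requirement.

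The cost is a wording change and different procedure calls, with no new data. Expect somewhat wider intervals and fewer nominally significant differences.

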#### 9.7.3.2 Multivariate analysis

The *primary analysis* will be conducted to investigate the risk of NDD, including ASD, in offspring paternally exposed to valproate (monotherapy) compared to lamotrigine or levetiracetam (composite monotherapy) treatment at the time of conception. All the analyses on NDD, including ASD, will only draw conclusions about NDD, including ASD, as a composite outcome, however a sensitivity analysis will focus on ASD alone (section 9.7.5).

The *secondary analysis* will be conducted to investigate the risk of CM in offspring paternally exposed to valproate (monotherapy), compared to lamotrigine or levetiracetam (composite monotherapy) treatment at the time of conception.

### **9.7.3.2.1 Effect estimation - Neurodevelopmental disorders, including autism**

A crude and a propensity-score (PS) weighted (section 9.7.3.2.3) Cox PH regression model will be used to estimate the HR of NDD, including ASD, with 95% CI (using offspring's calendar age in years as the underlying timescale) in offspring paternally exposed to valproate monotherapy within 3 months prior to LMP2 date compared to the reference group comprised of offspring paternally exposed to lamotrigine or levetiracetam (composite monotherapy) in the same time period. Inclusion of covariates not retained in the PS (section 9.7.3.2.2), in the Cox PH model will be considered in the event of imbalance in prognostically important variables. Covariates measured after index date will be included as time dependent in the Cox PH model, as appropriate. Post-estimation model diagnostics will be undertaken for each final parsimonious model, including log-log plots and Schoenfeld residuals, to assess the proportionality assumption.

Multiple offspring per father is possible and will introduce within-family dependencies into the data. Therefore in the analyses, paternal clustering will be taken into account by correcting standard errors with sandwich estimators (38). For purposes of the primary objective analysis for which the study is powered, a first Cox PH model will be estimated irrespective of clusters classification (section 9.3.1.3). This approach has the limitation to ignore intensity of exposure in the two exposure groups. To overcome this limitation, the first model will be repeated including the exposure intensity variable (estimated based on clusters as by application of k-means methodology (section 9.3.1.3)) as an effect modifier, i.e. the interaction exposure\*k-means will be included in the model. This second approach has the advantage of providing an estimate of the effect of paternal exposure to valproate vs the comparator group stratified by exposure intensity as measured by the k-means clusters.

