**Table 4: Potential confounding variables by outcome**

Outcome	Father
NDD, including ASD	
 
• Age
 
• Bipolar Affective Disorder and mania (ever)
 
• Calendar year of conception of offspring
 

CM	
 
• Age
 
• Calendar year of conception of offspring
 

NDD: Neurodevelopmental disorders; ASD: Autism Spectrum Disorder; CM: Congenital Malformations

**Paternal age.** Multiple epidemiological studies suggest a relationship between advanced paternal age at conception, and adverse neurodevelopmental outcomes (19,20) and congenital malformations (21–23) in offspring. This has been particularly noted with regard to increased risk for autism. ‘Paternal Age’ will be considered a confounding variable a priori, for both outcomes.

**Paternal Bipolar Affective Disorder and Mania.** Valproate is indicated in the treatment of epilepsy, mania and migraine (24). Moreover, children of parents diagnosed with mood disorders including mania have been shown to present with increased risk of neurodevelopmental outcomes. For these reasons, in this study, paternal bipolar affective disorder and mania will be considered as potentially confounding the effect of paternal valproate use on the development of neurodevelopmental disorders in offspring.

**Maternal epilepsy.** There is an increased risk of NDD, including ASD, and CM, in the offspring of female patients with epilepsy (25,26). However the high risk of NDD, including ASD in the offspring of female patients with epilepsy may be due to foetal exposure to AED medication in utero (2), including valproic acid. Offspring from women with epilepsy will only be included in the descriptive analyses of the sample from source population following data extraction, and excluded from the comparative, sensitivity and exploratory objective analyses.

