For the primary endpoint, the same assumptions exist with the exception that the assumed risk of NDD (including ASD) in the reference group is 4%. Therefore, in order to be able to observe a HR of 2.0 (i.e. doubling of risk in offspring paternally exposed to valproate) with 5% significance and 80% power, a sample size of 1178 offspring within the family linked unit would be needed across all three countries. This requires a minimum of 589 offspring within a family linked unit with paternal exposure to valproate (monotherapy), and a minimum of 589 offspring within a family linked unit with paternal exposure to lamotrigine/levetiracetam (monotherapy).

The eligible study cohort sizes are projected as follows:

---

diagnosed with epilepsy and/or treated with AEDs can be used for sample size assumptions. Furthermore, since a literature review reveals no equivalent estimates in Norway and Denmark, this estimate will be applied to Norway and Sweden to adjust feasibility counts.

Based on the aforementioned birth rate statistics and an assumption of 95% of births linked to fathers, an incidence rate of valproate monotherapy of 1.2/1000 patients and an incidence of 0.15% for childhood exposure to AEDs and/or diagnosis of epilepsy, we estimate an eligible population of offspring within a linked family unit with paternal valproate exposure of  $n \approx 940$  between 2004-2017 for Norway,  $n \approx 1495$  between 1995-2017 for Denmark, and  $n \approx 1645$  between 2005-2017 for Sweden. The estimated pooled eligible family linked offspring cohort for valproate monotherapy is 4,080 across all three countries.

If these projections are observed, this study should have a sufficient number of paternally exposed valproate offspring within each country to observe a HR of 2.0 for the primary endpoint of NDD, including ASD, with 5% significance and 80% power. It is also anticipated that this study would have a sufficient number of paternally exposed valproate offspring across all three countries to observe a HR of 2.0 for the endpoint of ASD (see sensitivity analysis section 9.7.5)

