Once the propensity scores are estimated (separately for the primary and secondary outcome cohorts) they will then be used as weights in the inverse probability of treatment weights approach to balance differences in covariate distribution between offspring paternally exposed to valproate and offspring paternally exposed to lamotrigine/levetiracetam in the adjusted analyses. PS weighting will be used instead of matching for increased generalisability and to avoid the exclusion of patients from the adjusted analyses due to lack of matches (43–46); this is deemed as particularly important in situations where the outcome of interest is relatively rare or infrequent.

For each PS model, the distributions of estimated propensity scores will be visually compared across the three models, separately for the primary and secondary outcome. Selection of the best models for the primary and secondary outcome cohorts will be based on the balance achieved in the weighted exposure groups after using inverse probability of treatment weights. Only the best PS models for the primary and secondary outcome cohorts will then be used to apply inverse probability of treatment weights in the multivariate analysis.

The best PS modelling approach might not be the same for the two cohorts, and similarly the covariates included in the PS model will differ as the two outcomes have different risk factors and confounders.

A sensitivity analysis to compare the results from the PS-weighted approach with the traditional approach of covariate adjustment will be performed, as reported in section 9.7.5, for both primary and secondary composite outcomes, using the composite lamotrigine/levetiracetam monotherapy comparator.

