8. *Validation of the assumption that individuals are exposed to one DDD per day.* WHO DDD is the assumed average maintenance dose per day for a drug used for its main indication (i.e. epilepsy for valproate, lamotrigine and levetiracetam) in adults. This does not necessarily reflect the recommended or Prescribed Daily Dose. Therapeutic doses for individual patients and patient groups will often differ from the DDD as they will be based on individual characteristics (such as indication, age, weight, ethnic differences, type and severity of disease) and pharmacokinetic considerations. A comparison (ratio) between the distribution of estimated treatment durations (expected) and time between prescriptions (observed) will be provided with the caveat that this will necessarily be affected by the DDD methodology approximation. In order to partially overcome this limitation, this comparison will be provided separately for patients with and without an indication of epilepsy, as epilepsy is the main indication for the medicines at study therefore the indication used by WHO to estimate DDD. It is expected that the use of WHO DDD will be a better approximation of the observed treatment duration among patients with a diagnosis of epilepsy, with a ratio closer to one than for other indications. The distribution of estimated treatment durations (expected) will be compared to the distribution of time between prescriptions (observed), *separately for lamotrigine, levetiracetam, valproate and for patients with and without an indication for epilepsy*, using the following formulas:

Observed time between prescriptions for patient i is

$$\sum_{j=1}^{k-1} \text{days} (\text{prescription}_{j+1} - \text{prescription}_j)$$

where k is the number of prescriptions for each patient.

Expected treatment duration for patient i is

$$\frac{\sum_{j=1}^{k-1} n. \text{pkg in prescription}_j * n. \text{dosage unit in each pkg}}{\text{WHO DDD}}$$

where k is the number of prescriptions for each patient.

The ratio of Observed over Expected for patient i is

$$\begin{aligned} \sum_{j=1}^{k-1} \text{days} (\text{prescription}_{j+1} - \text{prescription}_j) / \frac{\sum_{j=1}^{k-1} n. \text{pkg in prescription}_j * n. \text{dosage unit in each pkg}}{\text{WHO DDD}} &= \\ &= \sum_{j=1}^{k-1} \frac{\text{days} (\text{prescription}_{j+1} - \text{prescription}_j) * \text{WHO DDD}}{n. \text{pkg in prescription}_j * n. \text{dosage unit in each pkg}} \end{aligned}$$

The ratio for the population

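### Weights chosen for overall balance do not protect the exposure-by-intensity models: cluster-specific HRs and ORs can be confounded if the confounder-cluster link differs by drug

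*Protocol*

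**What the plan says.** Protocol 9.7.3.2.3 defines a PS for valproate against lamotrigine/levetiracetam, with a separate model for each outcome cohort. Intensity cluster is not part of what the PS models. Three modelling approaches are compared, and "Selection of the best models for the primary and secondary outcome cohorts will be based on the balance achieved in the weighted exposure groups". Only the chosen model then supplies the inverse probability weights for the multivariate analysis. Section 9.7.3.2, which carries that title, contains both the overall model and the cluster model.

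Section 9.7.3.2.1 fits the overall weighted Cox model first. This is the analysis for which the study is powered. It then repeats that model with the k-means cluster as an effect modifier: "the interaction exposure\*k-means will be included in the model". The gain claimed is a valproate effect stratified by exposure intensity. Section 9.7.3.2.2 builds the CM logistic model in the same way. Extra covariates may enter either outcome model, but only covariates that the PS did not retain.

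Three other statements bear on the point:
- Table 4 names "Bipolar Affective Disorder and mania (ever)" as a paternal confounder for NDD. For CM it lists only paternal age and calendar year.
- Section 9.7.5, item 8, says of the dose metric behind the clusters: "Therapeutic doses for individual patients and patient groups will often differ from the DDD". It gives indication as one reason and expects a better fit in epilepsy than in other indications.
- Section 9.7.5, item 5, says that the drugs may be prescribed for different indications, and that lamotrigine may be used in bipolar disorder while levetiracetam is not.

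**The concern.** Weights built on drug group alone equalise the confounder mix of the two drug groups taken whole. They do not do so once the groups are split by a third variable that is itself related to the confounder. Here that variable is the intensity cluster, formed from DDDs per 14-day interval. By the protocol's own account the fit of the DDD depends on indication, so cluster membership may carry information on indication, and it may do so differently for each drug.

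The cluster model is offered as the remedy for the first model's neglect of intensity, so readers will look for a gradient in its estimates. If bipolar disorder or mania is unevenly spread between the drugs inside a cluster, part of any gradient, or its absence, may reflect indication and not valproate. The covariate fallback would not help, because a confounder already in the PS falls outside it.

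**Working it through.** **The plan's own figure.** The protocol gives no figure for the cluster model. Its figure for the overall model reproduces. Inputs from section 9.5: "the assumed risk of NDD (including ASD) in the reference group is 4"%, and the aim to "observe a HR of 2.0 (i.e. doubling of risk in offspring paternally exposed to valproate"). Size: "with 5% significance and 80% power, a sample size of 1178 offspring within the family linked unit would be needed across all three countries". Section 9.7.3.1 sets the significance level "using 2-sided testing". By Freedman's formula:
- events = (1.960 + 0.842)² × ((1 + 2)/(1 − 2))² ≈ 7.849 × 9 = 70.6
- mean risk = (4% + 8%)/2 = 6%
- N = 70.64/0.06 = 1177.3, rounded up to 1178

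This supports the overall comparison only.

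**Balance within a cluster.** Let X be the confounder (for example bipolar disorder or mania) with prevalence p, and let the drug-only weights be exact, so that X has prevalence p in both weighted drug groups. Within cluster c, the weighted share of X in drug group a is

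s(a,c) = p·P(c|a,X=1) / [p·P(c|a,X=1) + (1 − p)·P(c|a,X=0)].

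If X multiplies the NDD risk by R and the drug has no effect, the apparent ratio in cluster c is

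[1 + s(valproate,c)(R − 1)] / [1 + s(comparator,c)(R − 1)].

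This is exactly 1 when P(c|a,X) does not depend on drug. It is also 1 when cluster is unrelated to X in each drug group.

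**One case in numbers.** Every input is assumed: p = 20%, R = 2; probability of the high cluster 0.3 (X) and 0.7 (no X) on valproate, 0.7 and 0.4 on the comparator.
- High cluster: valproate 0.06/(0.06 + 0.56) = 9.7%; comparator 0.14/(0.14 + 0.32) = 30.4%; ratio 1.097/1.304 = 0.84.
- Low cluster: valproate 0.14/(0.14 + 0.24) = 36.8%; comparator 0.06/(0.06 + 0.48) = 11.1%; ratio 1.368/1.111 = 1.23.

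**Range for p = 10% to 30% and R = 1.5 to 3, true HR 1 throughout.**

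| Confounder-cluster link | P(high), valproate: X / no X | P(high), comparator: X / no X | High cluster | Low cluster |
|---|---|---|---|---|
| Same in both drugs | 0.3 / 0.7 | 0.3 / 0.7 | 1.00 | 1.00 |
| Mild difference | 0.45 / 0.6 | 0.6 / 0.55 | 0.91 to 0.99 | 1.02 to 1.12 |
| Opposite | 0.3 / 0.7 | 0.7 / 0.4 | 0.71 to 0.95 | 1.08 to 1.48 |

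The direction follows from the assumed links. Exchanging the two drugs' links inverts the ratios.

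**Masking.** In the numbered case, true HRs of 1.6 (high) and 1.2 (low) would appear as 1.6 × 0.841 = 1.35 and 1.2 × 1.232 = 1.48, so the gradient reverses.

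**Simulation check.** 400,000 offspring, baseline risk 4% over 12 years, the inputs of the numbered case, probability of valproate 0.6 (X) or 0.3 (no X), true HR 1, weighted rate ratios:
- Crude overall ratio: 1.18.
- Drug-only weights: overall 1.00, with X at 20% in both groups; high cluster 0.84 (X 10% v 30%); low cluster 1.23 (X 37% v 11%).
- PS re-estimated within cluster: high 0.98, low 1.00.

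**The case against.** A reader might infer that the cluster-specific HRs *are* confounded. The protocol does not show that. Bias needs a confounder-cluster link that differs between drugs. Section 9.7.5 says that DDD fit depends on indication and that indications differ by drug, which makes a differing link plausible but does not establish it. The protocol gives no prevalence, no risk for bipolar fathers' offspring and no cluster distribution, so every magnitude above is assumed.

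It can also be said that unchanged weights are inferred, and that section 9.6.1 leaves analysis detail to the SAP, which was not available for this review. The inference is close, however: one selected PS per cohort is assigned to the whole multivariate analysis, and the second model is the first one repeated. Followed as written, the plan leaves within-cluster balance unprotected. A SAP could still add the missing step.

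A third objection is that the protocol puts its explicit dose-response work in sensitivity analysis 10. That analysis uses cumulative DDDs, forces covariates into the models, tests a drug-by-cumulative-exposure interaction and compares tertiles within each drug. This stands as partial mitigation, and it is why one cannot say that all intensity evidence is unreliable. It does not repair the cluster estimates, because it does not use the clusters, and the protocol says its three within-drug results are not comparable.

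Finally, cluster is measured in the same window as the drug and is part of the exposure, not a baseline covariate. Treating drug and intensity as one joint exposure would be an alternative. That affects the choice of remedy, not the need for one.

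**Conclusion.** The point holds in conditional form and is minor. The weights specified for the interaction models do not ensure balance between drugs within intensity clusters, so the cluster-specific estimates can be confounded, and a gradient created, hidden or reversed, if the confounder-cluster link differs by drug. Where it does not differ, the bias is nil. The calculated sizes rest wholly on the assumed prevalences, risk ratios and links: a few per cent up to about 12% in the low cluster for a mild difference, and up to 1.48 (low) or down to 0.71 (high) for opposite links.

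The indication example applies to NDD. The CM model shares the construction, but bipolar disorder is not a Table 4 confounder there, and no size was worked out for CM. It would be wrong to conclude that the powered primary HR is compromised: it does not use the clusters, and the weights are selected for exactly that comparison. Because the clusters assume one DDD per day, a gradient across them mostly reflects days covered and not daily dose.

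**What to change.** For the interaction models in 9.7.3.2.1 and 9.7.3.2.2 only:
- Re-estimate the weights with cluster and cluster-by-confounder terms in the PS. For NDD, use at least paternal age, bipolar disorder/mania and calendar year; for CM, paternal age and calendar year.
- Report weighted standardised differences between the drugs within each cluster.
- Label as descriptive any cluster-specific HR or OR for which balance is not acceptable, for example where a standardised difference exceeds 0.1.

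Leave the overall model and its weights as they are. The cost is an additional PS fit and balance table per outcome and country, if only the selected modelling approach is refitted, and more variable weights in small clusters. The number of clusters is not known in advance, so some may prove too small to balance; the descriptive label covers that case.
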